9. STUDY TIMELINES

The implementation of the intervention will start after all study materials have been finalized using feedback from focus groups (Aim 1) and community advisory boards. The intervention will be implemented in stages. This will allow for coordinated delivery of a physician education session approximately 1-2 weeks prior to each clinic starting the intervention. The intervention will be implemented in blocks of matched clinics, approximately one block every 1-3 months. We anticipate it taking approximately 6-12 months to complete the intervention at all sites. Patient participants will receive intermittent text messages over a period of approximately 3 weeks. We will examine vaccination status 12 weeks (primary outcome) and 6 months after the last text message to allow for possible lag between the intervention and vaccination. Because the vaccination status in the electronic health record is not immediately updated, these outcomes will be ascertained approximately 3 months after the timepoint in question to allow time for lag in the clinical system updating vaccination status. Therefore, the entire duration of the intervention for an individual patient participant will be approximately 52 weeks.

Provider participant involvement will occur over approximately 2 months.

This study is planned to take place over the course of 3 years, but may be extended if needed until all the tasks and deliverables are complete (see Table 1).

INVESTIGATOR STUDY PLAN - REQUIRED

Table 1: Study Timeline

Task	Year 1				Year 2				Year 3			
	Q1	Q2	Q3	Q4	Q1	Q2	Q3	Q4	Q1	Q2	Q3	Q4
Convene advisory panel, quarterly meetings	X	X	X	X	X	X	X	X	X	X	X	X
IRB approval	X											
Focus groups to refine messages & videos	X	X										
Video production & website creation			X									
Baseline data collection, including interviews	X	X	X									
Identification of study cohort			X									
Randomization of clinics			X									
Intervention – phased start				X	X	X	X	X				
Intervention data collection				X	X	X	X	X	X	X	X	X
Intervention evaluation							X	X	X	X	X	
Data analysis				X			X			X		X
Manuscript preparation									Ongoing			
Implementation guide creation & dissemination										X	X	X

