10. STUDY ENDPOINTS*

Primary Endpoint

The primary endpoint is the receipt of a complete COVID-19 vaccination series (2 doses for vaccines that require 2 doses) 12 weeks after the last text message, among patients who are unvaccinated at the time of clinic entry into the study.

Secondary Endpoints

Secondary endpoints include receipt of incomplete (1 dose for vaccines that require 2 doses) COVID-19 vaccination series; receipt of a complete COVID-19 vaccination series 6 months after the last text message; racial/ethnic differences in vaccination rates; and the percentage of intervention clinic patients who initiate vaccination after the first batch of provider texts, after the second batch of provider texts, and after the third batch of provider texts.

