The first batch of text messages will be delivered at the start of the intervention at a study clinic. Patients who have not been vaccinated against COVID-19 will receive messages from their PCP recommending the COVID-19 vaccine, with information on how and where to schedule a vaccination, and a link to a website with additional information and resources. The message content for each batch will be broken up into separate messages to ensure that the content is readable and not truncated by the texting system. Text message batches #2 and #3 (if applicable) will be sent approximately 1 week after the prior batch and will remind patients of the study website. The message content is included in appendix 1.

Text messages sent out in each batch will be professionally translated into multiple languages and provided in the patient’s preferred primary language, according to the capabilities of the clinical text messaging systems. Although messages will be automatically sent via a centralized

Figure 1. Aim 2 Study Activities

INVESTIGATOR STUDY PLAN - REQUIRED

system, they will indicate they are from the patient's PCP where possible. If it is not possible to include the PCP's name, the message will refer to the organization where the patient receives care. (See **Appendix 1** for text message content).

The website patients are directed to will be available in multiple languages via an embedded automatic translation feature. The provider videos will also be available in multiple languages via an automatic translation feature embedded in the website or video hosting platform.

Provider intervention

Providers at a study clinic randomized to the intervention will be asked to participate in a “lunch and learn” interactive session approximately 1-2 weeks prior to the start of the intervention. The session will be conducted either via video conference (e.g., Zoom) or in-person, depending on the state of the pandemic. An email inviting providers to these sessions is included in **Appendix 2**.

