Intervention Component	Details (what)	Recipient (who)	Timing (when)
Provider intervention			
Provider education	“Lunch and learn” interactive session to introduce study, underlying research supporting message content, and importance of provider recommendation for vaccination (appendix 3)	Providers at study clinic randomized to intervention	~ 1-2 weeks prior to intervention start at study clinic
Provider education	
 Emails with brief educational content (appendix 2): 
 Reminder of the study website and the resources available there Tip sheet for responding to patient questions and concerns (appendix 4) New scientific information as available 	Providers at study clinic randomized to intervention	~ Weekly x 3 during month that intervention starts at study clinic and if new resources or information is available thereafter
Patient intervention (appendix 1)			
Text message batch #1	Text messages from patient’s PCP or organization recommending COVID-19 vaccine and the study website (which contains the video library and information on how and where to get vaccinated).	Patients who have not been vaccinated against COVID-19 at time of study clinic entry	Delivered in a set at start of intervention at study clinic
Text message batch #2	Text messages from patient’s PCP or organization encouraging the patient to access the study website.	Patients who were unvaccinated at the start of the intervention	Delivered as a set approximately one week after first message
Text message batch #3	Text messages from patient’s PCP or organization encouraging the patient to visit the study website	Patients who were unvaccinated at the start of the intervention	Delivered as a set approximately one week after the second message

Control

Eligible patient participants seen at a study clinic randomized to the control group will receive usual care with no text intervention. Providers at a study clinic randomized to the control group will not be invited to attend the education session or sent any education materials. We are utilizing the Cluster Randomized design in an effort to control cross-group contamination.

EHR Data Collection

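### The date of clinic entry, which defines the primary cohort, is never stated; if it is the first text, the cohort is formed 1-2 weeks after the provider session has begun the intervention in one arm only

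*Combined protocol and SAP*

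**What the plan says.** Section 10 sets the primary endpoint as a completed vaccination series 12 weeks after the last text, "among patients who are unvaccinated at the time of clinic entry into the study". The data analysis plan in section 13 uses the same population and calls the analysis intention-to-treat. Neither section gives a date for clinic entry, for either arm.

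In section 11, Table 2 lists the provider session as the first intervention component and times it about "1-2 weeks prior to intervention start at study clinic". Section 9 agrees: "physician education session approximately 1-2 weeks prior to each clinic starting the intervention". On the other arm, section 11 says: "Providers at a study clinic randomized to the control group will not be invited to attend the education session".

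The start of the intervention is tied to texting: "The first batch of text messages will be delivered at the start of the intervention at a study clinic". Table 2 describes the recipients of batch 1 as "Patients who have not been vaccinated against COVID-19 at time of study clinic entry" and those of batches 2 and 3 as "Patients who were unvaccinated at the start of the intervention".

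**The concern.** The session is meant to be active: it teaches providers why their recommendation matters, and section 5 presents provider recommendation as consistently associated with uptake. If baseline status is read at the first text, it is read after this component has been delivered in one arm. A patient who accepts vaccination on a newly trained provider's advice during the gap is then already vaccinated at entry and is not analysed. The control clinic has no matching step.

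Membership of the primary analysis set would then depend on treatment. Intention-to-treat analysis keeps patients in the arm to which their clinic was randomized, but it does not restore patients who were never admitted to the cohort. There is also a plain reproducibility problem: with no entry date and no rule for doses given between session and first text, two analysts could build different primary cohorts from the same records.

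**Working it through.** **1. Which date is clinic entry?** The relevant places, side by side:

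| Place | What it indicates |
|---|---|
| Section 11, Table 2 | Batch 1 recipients are defined at clinic entry, batch 2 and 3 recipients at intervention start; these appear to be one group, so entry appears to be the first text |
| Section 13, power analysis | The 25% unvaccinated are counted at intervention start |
| Section 13, data analysis plan | Adjusts for vaccine availability when a clinic enters, so entry is clinic-specific and staggered |
| Section 9, Table 1 | The cohort is identified in Year 1 Q3, beside randomization and before the phased start in Q4, which allows an earlier date |
| Section 11, EHR data collection | Status of all patients is pulled at study start for matching; the check before each batch is in intervention clinics, to find text recipients |

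The first text is the likelier reading. It is not stated.

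**2. The plan's own figure.** Section 13 gives 5% versus 7.96%, a detectable difference of 2.96 points, at 80% power and two-sided 0.05. With individual randomization, n per arm = [1.96·√(2 × 0.0648 × 0.9352) + 0.842·√(0.05 × 0.95 + 0.0796 × 0.9204)]² / 0.0296² = 1,085. Available: 152,110 × 0.25 = 38,028 unvaccinated, or 19,014 per arm if the arms are equal, and 2,377 per clinic over 16 clinics. The implied design effect is 19,014 / 1,085 = 17.5. That corresponds to an intraclass correlation of about 0.0070 with equal clinic sizes, or 0.0035 with a coefficient of variation of 1.0. The plan states neither quantity, so 2.96 is plausible but cannot be confirmed.

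**3. Mechanism.** Let p be the intervention-arm proportion counted from before the session. Let a be the share of that arm vaccinated in the gap because of the session. A cohort formed at the first text shows (p − a)/(1 − a), so the difference shrinks by a(1 − p)/(1 − a), which is close to a. Background vaccinations leave both arms alike if the matched clinics share a date, and are omitted here.

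**4. Scale, by assumption only.** Suppose the total effect, counted from before the session, is 2.96 points, and a fraction f of it falls in the gap. The documents give no value for f. Even accrual means 1 of 15 weeks or 2 of 16 weeks: the gap, then about 2 weeks from first to third batch, then 12 weeks.

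| f | Points before entry (2.96 × f) | Difference seen | Patients of 19,014 |
|---|---|---|---|
| 2% | 0.06 | 2.91 | 11 |
| 1/15 = 6.7% | 0.20 | 2.78 | 38 |
| 2/16 = 12.5% | 0.37 | 2.62 | 70 |

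For the 2-week row: (7.96 − 0.37)/(1 − 0.0037) = 7.62, and 7.62 − 5 = 2.62. For comparison, background vaccination at 5% per 14 weeks would remove 5 × 1/14 = 0.36% to 5 × 2/14 = 0.71% of each arm, or 68 to 136 patients.

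**The case against.** The strongest reply is that the documents never say the cohort is fixed at the first text. The Table 2 cell describes who is texted, its timing column dates the texts rather than clinic entry, and Table 1 identifies the cohort before any clinic starts. This stands, and it is why the point is conditional. It does not remove the point. Blocks start 1-3 months apart over 6-12 months, so a single Q3 extraction cannot supply each clinic's status at its own staggered entry, and the study-start pull is described as serving matching.

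A reader might infer that planned power falls below 80%. The documents do not support that. Section 13 counts its unvaccinated patients, and hence the 2.96 points, from the start of the intervention. If that is the first text, doses in the gap were never part of the planned difference and cannot be subtracted from it.

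A reader might also infer that every gap vaccination is lost from the intervention arm alone. Only the extra, provider-prompted ones are.

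Even accrual is probably generous. Before the first text there are no texts, and the emails and tip sheets are scheduled for the intervention's first month. Session attendance is voluntary, and only patients in contact with a provider who attended can be affected. The plan also does not say whether one dose of a two-dose vaccine makes a patient vaccinated at entry. If it does not, someone with only a first dose in the gap stays in the cohort and can still become an outcome. Finally, section 9 notes that record updates lag, so a prospective status pull could miss some gap doses and keep those patients.

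**Conclusion.** The point holds conditionally. What is certain is that clinic entry has no date in either arm, that the provider session is a randomized component given in intervention clinics only, and that it precedes the first text by 1-2 weeks. If entry is the first text, the primary cohort is selected after exposure has begun in one arm, and the bias is toward no effect.

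Its size cannot be derived from the documents. It depends on how many unvaccinated patients meet a trained provider in the gap and on how a partial series is classified. The 0.20 to 0.37 points rest wholly on even accrual of an assumed 2.96-point effect, and the true loss is probably smaller. No power loss should be claimed. This is a cheap improvement, not a threat to the trial's validity.

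**What to change.** In sections 10, 11 (with Table 2) and 13:

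- Define clinic entry as one calendar date per matched pair, before the intervention clinic's first provider session and identical for its control clinic.
- Build the unvaccinated cohort retrospectively from recorded dose dates, because record status lags. State whether one dose of a two-dose vaccine counts as vaccinated.
- Count every series completed after that date as an outcome, up to the same outcome date in both clinics of the pair. The control clinic has no last text of its own from which to count 12 weeks.
- Use the check before each batch only to choose who is texted.
- Use one term for this date throughout, including for the 25% in the power paragraph.

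The cost is a change of definition. No new data source should be needed: reading a 12-week endpoint about 3 months late already requires dose dates in both arms. The downside is that a few cohort members will be vaccinated before the first text and will not be texted; they still count as outcomes in whichever arm they belong to. A sensitivity analysis with the cohort dated at the first text would show whether the choice matters.

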7. STUDY-WIDE NUMBER OF SUBJECTS*

Patient Participants

The intervention will be implemented at approximately 16 primary care clinics selected from three healthcare systems, including UMMHC, the Edward M. Kennedy Community Health

INVESTIGATOR STUDY PLAN - REQUIRED

Center (EMKCHC), and the Family Health Center of Worcester (FHCW). Eligible patients seen at a study clinic are at least 18 years of age or older. Based on the most recent data, there were approximately 152,110 adult (age \geq 18) patients seen in the selected primary care clinics at UMMHC, EMKCHC, and FHCW.

Provider Participants

Eligible providers are those who currently work at one of the primary care clinics selected from the three healthcare systems (UMMHC, EMKCHC, FHCW). Using information available on each healthcare system's website, we estimated that there are approximately 250 providers employed across the selected primary care clinics who will be eligible to participate in the provider education portion of the intervention. We will collect data from a subset of these providers, covered in IRB docket #H00023125.

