All Electronic Health Record (EHR) data pulls will be requested following the UMMS [Data Science Core](#) processes (currently located here: https://www.umassmed.edu/research-informatics/data_services/how-to-obtain-data/). EHR data will be pulled at non-UMMS sites according to their local institution-specific processes.

INVESTIGATOR STUDY PLAN - REQUIRED

COVID-19 vaccination status will be assessed via EHR on all patients seen at a study clinic to allow clinic matching by vaccination rate at study start. Prior to sending a batch of text messages, the COVID-19 vaccination status of patients in the intervention clinic will be re-assessed to identify those eligible to receive text messages, and their text communication preference will be extracted to allow those who have indicated they do not want to receive text messages to be filtered out.

Data related to the primary and secondary outcomes will be obtained via the EHR system following the completion of the intervention.

We will obtain additional data on all patients via the EHR to conduct supplemental analyses, including demographics (e.g., age, sex, race/ethnicity), text communication preference, text delivery status (delivered/undelivered), any response to study text messages, primary insurer, receipt of influenza vaccine, social vulnerability index (determined using patient address), and selected co-morbid medical conditions associated with risk of COVID-19 disease (e.g., hypertension, diabetes, obesity, congestive heart failure, chronic lung disease).

For additional details, see section 13. Data Analysis and Management.

Screenshots of the website, transcripts of the videos to be hosted on the website, factsheets that include video content adapted for print, and biographical sketches of the providers featured in the videos can be found in **appendices 6, 7, 8, and 9**. The factsheets were professionally translated and submitted to the IRB for review.

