12. DATA AND SPECIMEN BANKING*

No specimens are being collected as part of the research. A limited data set will be securely stored for potential future use by the Principal Investigator. We acknowledge that we will be collecting address information which cannot be included in a limited data set. This information will be used to determine the social vulnerability index and then it will be removed from the study data set. The address information will not be stored for future use. A de-identified data set will be shared upon request in accordance with NIH requirements for data sharing.

13. Data Analysis and Management*

SAMPLE SIZE

For details related to sample size, please see #7 Study-wide Number of Subjects.

POWER ANALYSIS

Power calculations employ two-sided hypothesis testing, 80% power, 0.05 Type I error, and account for within-clinic clustering and between-clinic variation in size. If 25% of patients are unvaccinated at the start of the intervention and 5% of control-clinic patients go on to receive a

INVESTIGATOR STUDY PLAN - REQUIRED

vaccination during the intervention period, we can detect an intervention-control difference of 2.96%, i.e., 7.96% of intervention-clinic patients become vaccinated. This is consistent with the effect size of other studies using a similar approach.¹⁰⁻¹²

DATA ANALYSIS PLAN

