The primary outcome of this study is receipt of a complete COVID-19 vaccination series (2 doses for vaccines that require 2 doses) among patients unvaccinated at a clinic's entry into the study, a binary outcome. We hypothesize that intervention-clinic patients receiving text messages from their provider will be more likely to receive a complete vaccination series than control-clinic patients. We will compare vaccination in patients from the two randomization arms using generalized linear mixed modeling,¹³ with a random effect for clinic to account for within-clinic clustering. In addition to estimating unadjusted between-randomization arm differences, we will adjust for key covariates, including study block as well as variables reflecting possible secular trends such as vaccine availability at the time of a clinic's entry into the study. Patient-level covariates will be available from the electronic health record (EHR), including age, sex/gender, insurance type, and address which will be used to determine the social vulnerability index; separate models also will adjust for race/ethnicity and relevant clinical diagnoses, both of which may be subject to more missing data than age and sex. In order to fully describe the population who did not receive the intervention (text messages), we will collect text communication preference, any responses to study text messages (to capture any patients responding "NO" to opt out of receiving further study text messages), and text delivery status (delivered/undelivered). We also will adjust for provider type (e.g., resident, attending, nurse practitioner) and time since last visit. In supplemental analyses, we will assess effect modification of the intervention-control difference by a) block, to explore whether intervention-control differences change over time; and b) provider type, to examine whether the impact of text message receipt varies by a patient's provider type. Analyses will be intention-to-treat.

Analyses for the secondary outcome of 1+ dose – also binary – will parallel the above analyses.

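### Influenza vaccination is extracted for every patient but not named as a covariate for the primary outcome; a pre-entry version belongs in the main adjusted model, for a modest gain

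*Combined protocol and SAP*

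**What the plan says.** Section 11, under EHR Data Collection, lists further fields to be taken from the record for all patients, described there as serving supplemental analyses. They include "primary insurer, receipt of influenza vaccine, social vulnerability index (determined using patient address". No time window is attached to the influenza field.

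Section 13, Data Analysis Plan, compares the arms on the primary outcome with a generalized linear mixed model that has clinic as a random effect. Unadjusted differences are to be reported. Adjusted ones account for study block, secular-trend variables such as vaccine availability, age, sex or gender, insurance type, social vulnerability index, provider type and time since last visit. For two further groups of variables, "separate models also will adjust for race/ethnicity and relevant clinical diagnoses, both of which may be subject to more missing data than age and sex". Text preference, delivery and replies are used to describe patients who were not reached. Influenza vaccination has no stated role in Section 13, and no model is named as the main one.

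The power statement reads "Power calculations employ two-sided hypothesis testing, 80% power, 0.05 Type I error" and is said to "account for within-clinic clustering and between-clinic variation in size". It concludes that "we can detect an intervention-control difference of 2.96%, i.e., 7.96% of intervention-clinic patients become vaccinated".

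**The concern.** Whether a person has accepted another vaccine is a plausible predictor of whether that person will accept this one. The field is already being extracted for both arms, and it is the only one in the Section 11 list that cannot be traced to a use in Section 13. If it predicts uptake, and if clinics differ in it, leaving it out gives up some precision in a trial with about eight clinics per arm.

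Silence also has a cost of its own. A field that is on file but unassigned can be added to the model, or left out, after outcomes are known. And because no window is given, it could be added in an unsafe form. Intervention-clinic providers receive training and materials on talking with vaccine-hesitant patients, and control-clinic providers do not. An influenza dose given after clinic entry could therefore be a consequence of the intervention, and adjusting for it could bias the comparison.

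**Working it through.** **Inputs from the documents.** Section 7 gives "approximately 16 primary care clinics selected from three healthcare systems" and "approximately 152,110 adult" patients. Section 13 gives 25% unvaccinated, 5% uptake in control clinics and 7.96% in intervention clinics. No intracluster correlation (ICC) or coefficient of variation (CV) of clinic size is given.

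**Step 1: what the plan's 2.96 implies.**
- Unvaccinated patients: 152,110 × 0.25 = 38,027.5, which is about 19,014 per arm and 2,377 per clinic.
- Standard error needed for 80% power: 2.96 / (1.960 + 0.842) = 1.057 points.
- Variance without clustering: (0.05 × 0.95 + 0.0796 × 0.9204) / 19,014 = 0.12076 / 19,014 = 6.35 × 10⁻⁶.
- Implied design effect: 0.01057² / (6.35 × 10⁻⁶) ≈ 17.6. With t quantiles it is 15.2 (14 df) or 13.0 (7 df).
- Implied ICC with equal clinic sizes: (17.58 − 1) / (2,377 − 1) = 0.0070. Across the t variants and a CV of 0 to 1 it runs from 0.0025 to 0.0070.

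The stated 2.96 is therefore attainable, but it cannot be confirmed without the ICC and CV.

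**Step 2: where the variance lies.** The within-clinic share is (1 − ICC) / design effect = 0.993 / 17.58 = 5.7%, or up to 7.7% with t quantiles. So 92-94% is between clinics. If a covariate explained 5-20% of the within-clinic part only, the detectable difference would be 2.96-2.94 and power 80.1-80.5%. A useful gain requires the covariate to explain why clinics differ.

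**Step 3: simple formula for influenza vaccination (all strengths assumed).** On the logit scale the implied between-clinic SD is √(0.0070 / (0.065 × 0.935)) = 0.339, where 6.5% is the mean uptake. The share explained is f = (SD of clinic prevalence × log odds ratio)² / 0.339². The detectable difference is 2.96 × √(1 − 0.943 f).
- Low (SD 5 points, log odds ratio 0.8): f = 0.0016 / 0.1149 = 1.4%, giving 2.94.
- Middle (SD 10 points, log odds ratio 1.0): f = 0.0100 / 0.1149 = 8.7%, giving 2.84.

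**Step 4: simulation.** The settings were 16 equal clinics of 2,377, between-clinic logit SD 0.33, 35% prior influenza vaccination, 4,000 runs per setting, and a two-stage residual adjustment on the risk-difference scale. The last column multiplies 2.96 by the ratio.

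| Clinic logit SD of influenza uptake | Odds ratio | SE adjusted / unadjusted | Detectable difference |
|---|---|---|---|
| 0 | 2 | 0.999 | 2.96 |
| 0 | 3 | 1.000 | 2.96 |
| 0.2 | 2 | 0.995 | 2.95 |
| 0.2 | 3 | 0.986 | 2.92 |
| 0.4 | 2 | 0.977 | 2.89 |
| 0.4 | 3 | 0.949 | 2.81 |

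At 35% prevalence a logit SD of 0.2 is about 0.2 × 0.35 × 0.65 = 4.6 points, and 0.4 is about 9.1 points, so the two methods agree in size. At the best ratio, power is Φ(2.802 / 0.949 − 1.960) = Φ(0.99), about 84% instead of 80%.

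**The case against.** The case for leaving the plan alone has real force. The covariate lists in Section 13 are worded as examples, so influenza vaccination is unnamed rather than excluded. Section 11 assigns the extra fields to supplemental analyses, and a trial need not use every extracted field in its primary model. Clinics are matched on site, baseline COVID-19 vaccination rate and vaccine availability before randomization within pairs (Section 11, Randomization). The planned covariates may also overlap with influenza uptake. Steps 3 and 4 credit influenza vaccination as if none of this were present. All of that stands, and it limits the size of the point. The supplemental label does not fully account for the omission, since the same list holds age, sex and insurer, which are adjusters.

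Three stronger readings are tempting, and the documents support none of them.

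- A reader might infer that substantial precision is being thrown away. Combining the largest assumed clinic SD (15 points) with the largest log odds ratio (1.2) gives f = 0.0324 / 0.1149 = 28% and a detectable difference of 2.54. That is one corner of an assumed range, with no allowance for overlap or matching.
- A reader might infer that placing race/ethnicity and diagnoses in separate models is a fault, or breaches intention-to-treat. The plan gives its reason, missing data. Separation keeps patients with missing values in the main model and confines any loss to the additional ones. Adding an unknown category instead is debatable, and is poorly defined for diagnoses if an unrecorded condition cannot be told from an absent one.
- A reader might infer that the influenza data will be drawn after the intervention. Section 11 lists fields without dating the extraction. The pre-entry restriction is needed because no window is stated, not because a late extraction is documented.

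**Conclusion.** The point holds as a low-cost improvement, not as an error in the plan. A plausible predictor of the primary outcome is on file for every patient and has no assigned role, and no adjusted analysis is designated as the main one.

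The expected gain is a standard error about 0-5% smaller, or a detectable difference of roughly 2.8-2.96 points instead of 2.96. This assumes 35% prior influenza vaccination, an odds ratio of 2-3, a clinic SD of up to about 9 points and equal clinic sizes. None of these figures comes from the documents. The gain is near zero if clinics do not differ in influenza uptake, or if the matching and planned covariates already carry the information. An ICC below 0.0070 would raise the share that the same covariate explains. The documents allow neither effect to be sized.

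The link function is not stated. With a logit link, adding a covariate also changes the conditional odds ratio, so any gain should be judged on a marginal risk difference rather than on the standard error of the log odds ratio.

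**What to change.** In Section 13, Data Analysis Plan:

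1. Add to the patient-level covariates: influenza vaccination in the last full season before clinic entry (yes/no), counting only doses dated before entry. For control clinics, define entry as the start date of their matched block, so that the window is the same in both arms.
2. Name the model with the planned covariates plus this one as the main adjusted analysis, before outcome data are examined.
3. Keep the separate models for race/ethnicity and diagnoses, labelled as sensitivity analyses.

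In Section 11, state that influenza dose dates are extracted, not only receipt.

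The cost is wording and a date field. The variable is already requested, and the analysis file is already planned as a limited data set that holds dates. No change to sample size, randomization or patient contact is needed.
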